patient safety and outcomes. Of note, Doppler ultrasound has already been used to monitor flaps [Rosenberg JJ, Fornage BD, and Chevray PM 2006 Monitoring Buried Free Flaps: Limitations of the Implantable Doppler and Use of Color Duplex Sonography as a Confirmatory Test, Vakharia KT, Henstrom D, Lindsay R, Cunnane MB, Cheney M, and Hadlock T 2012 Color Doppler Ultrasound: Effective Monitoring of the Buried Free Flap in Facial Reanimation]. However, there is little comparative data versus other methods of monitoring. This study is primarily aimed at collecting data assessing the performance of Doppler ultrasound monitoring with EchoMark in a more quantitative way.

Device Description

ECHOMARK

The EchoMark is an echogenic polymeric marker used to mark surgical sites with ultrasound. The device has a specially designed form factor that provides intuitive, continuous changes in its two-dimensional ultrasound outline when imaged from different angles and positions. EchoMark is produced with a manufacturing technique that enhances acoustic resonance to maximize brightness under ultrasound. EchoMark is composed of a bioresorbable polymer with a long history of use in sutures and medical devices and dissolves within 18-24 months.

ECHOSURE

EchoSure is a Doppler ultrasound device that automatically delivers visual and quantitative blood flow information, and may be utilized intraoperatively or postoperatively from the bedside by a nurse or other healthcare provider without the need for special sonographic training.

Benefits

EchoMark and EchoSure together enable the patient care team to collect critical blood flow information intraoperatively and during routine patient examinations postoperatively. The technology displays both a visual indication of arterial and venous blood flow in real-time and provides the quantitative changes in volumetric flow rate in each vessel. This information is critical for:

- Detecting vascular compromise early enough for flap salvage
- Delivering reliable information to eliminate false positives and unnecessary take-backs to the OR
- Selecting optimal vessels for free flap surgery, and
- Diagnosing potential issues intraoperatively prior to leaving the OR

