5. STUDY OBJECTIVES

Purpose

The purpose of this study is to evaluate the performance of the EchoMark and EchoSure (both FDA approved devices) as an ultrasound-based method of monitoring the viability of free flaps and patency of at-risk vessels. The implant and ultrasound will be used per IFU. The primary purpose of the study is to collect data on patient outcomes in cases where the surgeon has chosen it as the appropriate method of monitoring.

Performance Goals

Primary Performance Endpoint:

- Surgeon evaluation of improved monitoring ability and satisfaction

Secondary Performance Endpoints:

- Flap failure rate
- Flap takeback rate
- Flap salvage rate
- Total cost of hospitalization
- Time from OR departure to return to OR
- Nurse evaluation of improved monitoring

Safety Goals

Primary Safety Endpoint:

- Procedure freedom from Serious Adverse Events (SAEs) during the EchoMark implantation procedure, hospitalization, and at discharge.

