7. STUDY POPULATION

Number of Patients

Up to four hundred (400) patients will be enrolled and both men and women will be eligible for inclusion. The estimated enrollment period is nine months and patients will be followed until discharge from their index surgical procedure.

Intended Use

The EchoMark and EchoSure devices are intended to be used by a trained medical professional. The EchoMark device is intended to be a Single Use Device, used in a surgical operating suite or equivalent setting. The EchoSure device is reusable and may be used in the operating suite or a post-operative unit such as the ICU or patient floor. When used intraoperatively or in the presence of breached skin, the EchoSure Probe should be used with a sterile probe cover.

Inclusion Criteria

- Age \geq 18 years

- Patients presenting for microvascular tissue transfer procedures where the surgeon has selected EchoMark and EchoSure as the optimal method of vascular monitoring based on clinical assessment and plan
- Patient is able to sign informed consent and able to participate in all testing associated with this clinical investigation
- Women of childbearing potential have a negative pregnancy test

Exclusion Criteria

- Age <18 years old
- Patient unable to sign informed consent
- Patient participating in another investigational device or pharmacological study
- Prisoner or patient from vulnerable populations as defined in 45 CFR 46.

PATIENT WITHDRAWAL FROM THE STUDY

Patients are free to withdraw consent at any time. Patients who wish to terminate their participation in the research will no longer receive ultrasound examinations of their free flap and their data will be removed from the study.

8: STATISTICAL ANALYSIS

Statistical power was calculated based on determination of the number of detected thrombosis events needed to see a difference between EchoSure and an alternate method of flap monitoring (e.g., clinical examination). A one-tailed paired t-test was used to compare the dichotomous outcome of whether EchoSure detected a thrombotic event prior to other methods of monitoring. At $\alpha=0.05$ and $\beta=0.80$ with a medium Cohen's effect size of 0.5, 27 thrombotic events are needed for comparison. With a baseline national re-exploration rate of about 7%, an enrollment of 385 patients will provide sufficient sample size for the analysis.

9: PATIENT ENROLLMENT AND CONSENT

Method of Subject Identification and Recruitment

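### Section 8 counts its requirement in thromboses but converts it to patients with a re-exploration rate, so the claim that 385 patients suffice rests on an unstated, near-complete overlap of the two

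*Combined protocol and SAP*

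**What the plan says.** Section 8 (Statistical Analysis) bases power on "the number of detected thrombosis events needed to see a difference between EchoSure and an alternate method of flap monitoring". With a one-sided paired t-test and the inputs "At $\alpha=0.05$ and $\beta=0.80$ with a medium Cohen's effect size of 0.5", it concludes that "27 thrombotic events are needed for comparison". It then moves from events to patients in one sentence: "With a baseline national re-exploration rate of about 7%, an enrollment of 385 patients will provide sufficient sample size for the analysis". No definition or source is given for the 7%. No thrombosis rate appears anywhere, nor any share of re-explorations that are thromboses.

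Three other places bear on that step:

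- Section 7, Number of Patients, sets the ceiling: "Up to four hundred (400) patients will be enrolled".
- Section 7, on withdrawal, says of patients who withdraw that "their data will be removed from the study".
- Section 4, Benefits, lists as a use of the device's information: "Delivering reliable information to eliminate false positives and unnecessary take-backs to the OR".

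Section 5 lists "Flap takeback rate" among the secondary endpoints, but no thrombosis endpoint and no comparison of detection times.

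**The concern.** The numerator and the rate refer to different events. A return to the operating room is a decision by the surgical team; a thrombosis is a finding. Section 4 itself accepts that some returns are unnecessary. If the 7% counts returns of every cause, the number of thromboses among 385 patients will be smaller than the number of re-explorations, by an amount that the plan does not state.

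This is the only sample-size justification in the documents, and it is worded without condition. A reader cannot see that it depends on an overlap close to complete, or that 385 enrolled patients leave no room for removed data. What is at stake is the sample-size justification and the Section 8 comparison of EchoSure with other monitoring. The listed performance and safety endpoints are not affected.

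**Working it through.** **Inputs from the documents.** One-sided alpha 0.05; power 0.80 (printed as beta, and read as power because that reading gives 27); d = 0.5; 27 events; re-exploration rate about 7%; enrollment 385, capped at 400 (Sections 7 and 8).

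**Inputs assumed here.** The thrombotic share f of re-explorations (100, 90, 70 and 50%), and 6.5 to 7.5% as a reading of about 7%. Neither is in the documents.

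**Step 1: the plan's own figures.** Exact noncentral-t power for a one-sided paired t-test with d = 0.5 is 0.798 at 26 events, 0.812 at 27 and 0.825 at 28. So 27 reproduces. For patients, 27 / 0.07 = 385.7, against 385 stated. The whole 7% was therefore used as the thrombosis rate.

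**Step 2: the share that this requires.** Required share = 27 / (N × rate).

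- N = 385: 385 × 0.07 = 26.95; 27 / 26.95 = 100.2%.
- N = 400: 400 × 0.07 = 28.0; 27 / 28 = 96.4%.
- At 7.5%: 27 / 28.875 = 93.5% (385) and 27 / 30 = 90% (400).
- At 6.5%: 27 / 25.025 = 108% (385) and 27 / 26 = 104% (400), so 27 is not expected even if every re-exploration is a thrombosis.

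Because the rate is given only as about 7%, these are best read as roughly 95 to 100%, not to a tenth of a percent.

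**Step 3: withdrawals.** At f = 100%, 386 analysed patients are needed (385.7 rounded up). Enrolling 385 leaves no allowance; enrolling 400 leaves 400 − 386 = 14, or 3.5%.

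**Step 4: what other shares would mean.** Expected events = N × 0.07 × f. The event count is taken as Binomial(N, 0.07 f), and the power of the plan's t-test is averaged over that count. All N patients are taken as analysed. Each cell gives 385 / 400.

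| Share f | Expected thromboses | Chance of at least 27 | Average power, plan's own test |
|---|---|---|---|
| 100% | 26.95 / 28.0 | 0.52 / 0.61 | 0.80 / 0.81 |
| 90% | 24.3 / 25.2 | 0.31 / 0.38 | 0.76 / 0.78 |
| 70% | 18.9 / 19.6 | 0.04 / 0.06 | 0.66 / 0.68 |
| 50% | 13.5 / 14.0 | 0.001 / 0.001 | 0.53 / 0.54 |

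The power column only sizes the mismatch on the plan's own terms.

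**Step 5: why those power values should not enter the protocol.** The outcome is dichotomous. Score each event +1 if EchoSure was first and −1 otherwise. Then d = (2p − 1) / (2√(p(1 − p))) = 0.5 gives p = 0.724. An exact one-sided binomial test at 27 events needs at least 19 successes (null probability 0.026; 18 would give 0.061), and its power is 0.68, not 0.80.

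**The case against.** The strongest reply is that no shortfall has been shown. The documents give no thrombotic share; at 100% the average power is 0.80, and the 7% may already count only re-explorations for thrombosis. The bullet in Section 4 describes a hoped-for benefit, carries no frequency and does not say what the 7% counts. Power also falls gradually: 26 events instead of 27 costs little more than one point, and a 90% share costs about four points. Thromboses detected without a re-exploration, or a higher rate in this surgeon-selected population, would ease the requirement further. Finally, the comparison is not a listed endpoint, and the study is a single-arm observational one.

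Most of this stands, and it limits the point. It does not rescue the sentence as written, because the plan states none of these conditions and declares sufficiency without any.

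Three stronger readings are tempting, and the documents do not support them. A reader might infer an arithmetic error, but the division is correct to within rounding. A reader might infer that the study is underpowered by a known amount, but that needs a share that is not given. A reader might treat 27 as a threshold below which the comparison fails, but the table shows a slope.

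**Conclusion.** The concern holds as an event mismatch in a sample-size assumption, of minor to moderate severity. The plan's figures support 385 patients only if re-explorations and detected thromboses are practically the same events and almost nobody's data are removed. The documents state neither condition, and Section 4 gives some reason to doubt the first.

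The mismatch in wording is certain. The size of its effect is not: it depends on the assumed share, on about 7% being the right rate for this population, and on thromboses being a subset of re-explorations. The loss is nil or slight when the share is close to complete. It becomes material at shares near 70% or below, where the expected number of events drops by about a quarter to a half.

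**What to change.** In Section 8:

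1. Define and source the 7%, including which returns to the operating room it counts. If it already counts only re-explorations for thrombosis, one clause saying so settles the event mismatch.
2. Otherwise convert events to patients with a thrombosis rate, or with the re-exploration rate multiplied by an explicit thrombotic share. Apply it to analysed patients, meaning enrolled minus withdrawn.
3. Replace the unconditional sufficiency claim with a conditional one, for example: *If the re-exploration rate is about 7%, about 27 thrombotic events are expected among 386 analysed patients only if every re-exploration is a detected thrombosis; about 19 are expected if 70% are.* The 70% is illustrative (386 × 0.07 × 0.70 = 18.9) and should give way to the sourced share.
4. Do not restate 80% power at 27 events. Recompute any power figure for the test that will actually be used on the dichotomous outcome.

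The cost is a rewording plus one definition and one sourced or openly assumed input. No extra patients or visits are requested. The downside is a less favourable, conditional statement.

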10. STUDY PROCEDURES AND METHODS

Patients undergoing free flap procedures will be identified. No additional clinic visits or additional hospital stay will be required of any study participant. All monitoring of skin or soft tissue will be carried out in the same manner. EchoMark will be implanted prior to closing the patient following the Instructions for Use on the FDA-approved labelling.

The flap will be non-invasively monitored with the EchoSure ultrasound intraoperatively and postoperatively. Intermittent ultrasound monitoring will be performed postoperatively at the institutional standard flap check protocol (q1 hours in first 24 hours, q2 hours in hours 24-48, and q4 hours thereafter) until the patient is discharged from the hospital. Presence of arterial and venous flow will be recorded. Images and/or video clips will be saved.

Actions to Be Taken by Site Staff	Screening and pre-operative evaluation	Surgery Date	Each Scan	Discharge
Consenting	X			
Initial Enrollment Form		X		
Nurse Scan Form		X	X	
EchoSure Scan			X	
Standard Clinical Exam			X	
End of Trial Period Form				X

11: DATA COLLECTION, ANALYSIS, AND MONITORING

Participating surgeons and nurses will complete a brief survey (see CRFs in appendix) capturing their assessment of whether they felt EchoMark and EchoSure improved their ability to monitor free flaps. Surgeons will complete a short form detailing the clinical characteristics and outcome of the case (e.g., whether there was a vascular flow problem and how it was detected). This, and the data management and storage, will be managed by the PI.

Source Documentation

The Investigator must maintain complete source documents on all trial patients who are enrolled in the trial or who undergo screening. Source documents include patient medical records, hospital charts, clinic charts, Investigator's patient trial files, as well as the results of diagnostic tests (e.g., laboratory tests) kept in an individual patient binder and stored in a secured and locked location and must be made available to the sponsor or designated monitor during site visits.

The following minimum information should be recorded in the patient's medical records:

- The date the patient entered the trial and the patient number
- The trial protocol number and the name of the Sponsor
- The date that informed consent was obtained
- Evidence that the patient meets trial eligibility requirements (e.g., medical history, trial procedures and/or evaluations)
- The dates of all trial related patient visits
- Evidence that required procedures and/or evaluations were completed
- Documentation of specific device used, if any
- Occurrence and status of any Adverse Events
- The date the patient exited the trial, and a notation as to whether the patient completed the trial or was discontinued, including the reason for discontinuation

DATA QUALITY ASSURANCE

Case Report Forms specific to the Observational Study of Outcomes after EchoMark and EchoSure-based Free Flap Monitoring trial will be used for the collection and recording of data at the Investigational site. Investigators are responsible for the timely completion and storage of these forms.

All CRFs will be collected by the Investigator and entered into a database. All case report forms received will be reviewed, tracked and filed. Prior to data entry, a pre-entry review will be conducted to ensure that mandatory fields have been completed. Incoming data will be reviewed to identify inconsistent or missing data. All hard copy forms and data files will be secured to ensure confidentiality.

Investigators are to maintain all source documents, including diagnostic test reports, laboratory results, completed case report forms, supporting medical records and informed consent. The source documents will be referenced during monitoring visits to verify the information documented on the case report forms.

PATIENT CONFIDENTIALITY

All information concerning patients or their participation in this trial will be considered confidential. Only authorized Sonavex personnel and designated consultants and regulatory agencies will have access to these confidential files. Enrolled patients will be assigned a unique identifier that will be used to maintain confidentiality of each patient's medical information. Patient names and other protected health information will not be captured on the case report forms.
